the Confusion Assessment Measure (CAM) or the ICU Confusion Assessment Measure (CAM-ICU) for both preoperative and postoperative periods (over 7 consecutive days). Early cognitive function was screened using the Mini-Mental State Examination (MMSE) on preoperative day 1, postoperative day 3, and postoperative day 7. Sleep quality was evaluated using the Richards-Campbell Sleep Questionnaire (RCSQ) on preoperative day 1, postoperative day 1 morning, and postoperative day 3 morning to assess prior night sleep status. Recovery quality was scored using the 15-item Quality of Recovery Scale (QoR-15) on preoperative day 1, postoperative day 1, postoperative day 3, and postoperative day 7. Pain and analgesic demand were recorded as baseline pain levels on preoperative day 1 and pain numerical scores (NRS) within 48 hours postoperatively (recorded at least once daily), along with total opioid consumption within 48 hours postoperatively (converted to oral morphine equivalents).

7) Perioperative complications and mortality rate

The incidence rates of cardiovascular complications (including new-onset atrial fibrillation and other arrhythmias, acute myocardial infarction, postoperative myocardial injury, and low cardiac output syndrome), stroke, pulmonary embolism, pulmonary infection, deep vein thrombosis, surgical site deep infection, and all-cause mortality within 30 days postoperatively.

8) Resource consumption

Length of hospital stay, ICU stay duration, and re-admission rate due to complications.

9) Biomarkers

To comprehensively evaluate patient status and explore the pathogenesis of AKI, this study detected the following biomarkers:

a) Routine testing: Collect daily routine laboratory data before surgery and for 7 days postoperatively, including C-reactive protein (CRP), neutrophil-to-lymphocyte ratio (NLR), cardiac troponin (cTn), creatine kinase isoenzyme MB (CK-MB), N-terminal pro-brain natriuretic peptide (NT-proBNP), and serum cystatin C.

b) Specific inflammatory markers and renal injury indicators: Peripheral blood samples were collected at 24h, 48h, and 72h postoperatively and placed in EDTA anticoagulation tubes. Plasma interleukin-6 (IL-6) and neutrophil gelatinase-associated lipocalin (NGAL) concentrations were detected in batches using the ELISA method.

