c) Peripheral blood immune cell phenotype analysis: Peripheral blood samples were collected at 24h, 48h, and 72h postoperatively and placed in EDTA anticoagulation tubes. Peripheral blood mononuclear cells (PBMCs) were isolated within 4 hours. Multicolor flow cytometry was employed to detect the expression level of $\alpha 7$ nAChR on the surface of CD14⁺ monocytes and the proportion of intracellular IL-6⁺, as well as the proportions of Th17 (IL-17A⁺) and Treg (CD25⁺CD127^{low/-}) subsets among CD4⁺ T cells, with the Th17/Treg ratio calculated. The analysis was performed using a CytoFLEX flow cytometer and FlowJo software.

Note: Items b and c represent exploratory additional testing mechanisms. A total of 40 patients were selected from the overall sample using stratified random sampling for additional diagnostic evaluation items. The stratification factors included group assignment and Cleveland Clinic score-predicted risk level of dialysis-dependent AKI.

All samples were processed and analyzed using a blinded method. All blood samples were aliquoted into low adsorption cryovials (0.5 mL/vial) to avoid repeated freeze-thaw cycles, and immediately stored in an ultra-low temperature freezer at -80 ° C. Complete sample numbering and time records were established. Upon study completion, the samples were disposed of in accordance with medical waste disposal standards.

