GEE were employed to analyze differences in the temporal variation trajectories of routine laboratory parameters and plasma IL-6/NGAL levels between two groups. The model included grouping, time, and their interaction as fixed effects, with subjects as random effects. Appropriate work-related matrices and distribution families were selected to assess the significance of the group \times time interaction. Independent samples t-test or Mann-Whitney U test was used to compare postoperative monocyte α 7nAChR expression levels, intracellular IL-6+ proportion, and Th17/Treg ratio at various time points between the two groups. GEE analysis was also conducted to evaluate overall trends and intergroup differences. Spearman correlation analysis was employed to investigate associations between immune cell markers (α 7nAChR, IL-6+, Th17/Treg), plasma biomarkers (IL-6, NGAL), and clinical outcomes (AKI incidence rate, peak serum creatinine level).

[figure not shown]
To determine the minimum number of stimulation days required to achieve clinical efficacy, the completion of stimulation was defined as when the actual daily stimulation duration reached $\geq 80\%$ of the planned duration. Based on the total number of days (0-6 days) during which subjects completed stimulation, a multivariate logistic regression analysis was performed to examine the dose-response relationship between cumulative stimulation days and the incidence of AKI, thereby identifying the critical number of days when the protective effect tends to plateau.

Subgroup analysis was conducted based on the following prespecified factors: gender, left ventricular ejection fraction (<35% vs. $\geq 35\%$), age (<65 years vs. ≥ 65 years), preoperative eGFR (<90 vs. ≥ 90 mL/min/1.73 m²), CPB duration (<120 min vs. ≥ 120 min), and surgical type (high-risk group [valve and coronary artery combined/aortic surgery] vs. low-to-moderate risk group [valve and septal repair]). Subgroup analysis was implemented in single-factor logistic regression models by introducing interaction terms between grouping and subgroup variables, with OR values and 95% CI for each subgroup visually presented in forest plots.

Safety analysis was based on the safety dataset (all subjects who received at least one stimulation). The incidence rates of all adverse events and serious adverse events were compared between groups using the χ^2 test or Fisher's exact probability method.

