Unless otherwise specified, all tests were conducted as two-tailed tests with a significance level set at $\alpha = 0.05$, meaning that differences were considered statistically significant when $P < 0.05$.

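### No small-sample method is given for the GEE analyses: with the usual sandwich Wald test, the group-by-time test has a real size of about 7.6% in the exploratory 40-patient set and 7.3% for the eight-time laboratory data

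*Combined protocol and SAP*

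**What the plan says.** Section 3.3.2.2, item 9, lists three groups of biomarkers. Routine laboratory values (item a) are collected before surgery and on each of seven postoperative days, in all patients. For items b (plasma IL-6, NGAL) and c (flow cytometry), "Peripheral blood samples were collected at 24h, 48h, and 72h postoperatively and placed in EDTA anticoagulation tubes". Items b and c are restricted to a subset: "A total of 40 patients were selected from the overall sample using stratified random sampling for additional diagnostic evaluation items". The same note states their status: "Items b and c represent exploratory additional testing mechanisms".

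Section 3.3.3 puts the routine laboratory values and IL-6/NGAL under one GEE specification: "The model included grouping, time, and their interaction as fixed effects, with subjects as random effects". It continues: "Appropriate work-related matrices and distribution families were selected to assess the significance of the group" by time interaction. The flow markers are compared at each time by t-test or Mann-Whitney, and then "GEE analysis was also conducted to evaluate overall trends and intergroup differences".

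The section closes by setting a two-sided 0.05 level for all tests unless otherwise specified, "meaning that differences were considered statistically significant when" P is below 0.05. It names no variance estimator, finite-sample correction or reference distribution for any GEE.

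**The concern.** The usual GEE test divides an estimate by a sandwich standard error and refers the squared ratio, or its multi-df version, to chi-square. This is justified when there are many independent subjects relative to the number of contrasts tested. With few subjects the sandwich is biased downward, and chi-square ignores the uncertainty in the estimated covariance. P values are then too small and intervals too narrow.

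The only modelling choices the plan leaves open are the working correlation and the distribution family. With complete data, an identity link and a separate mean for each arm at each time, neither the estimates nor the sandwich depend on the working correlation. Choosing it carefully therefore does not help.

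At stake is the false-positive rate for statements about mechanism. IL-6 and NGAL are the most exposed because GEE is their only planned between-group test.

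**Working it through.** **Inputs from the documents.** 40 patients in the subset; three postoperative samples with no baseline sample; eight samples for the routine laboratory values (one before surgery, seven after); 76 patients per arm enrolled and 68 per arm before the dropout allowance (section IV); two-sided 0.05.

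**Assumed.** The documents do not give the split of the 40 by arm. They say only: "The stratification factors included group assignment and Cleveland Clinic score-predicted risk level of dialysis-dependent AKI". I take 20 and 20 and vary this below. I also assume an uncorrected sandwich, a Wald chi-square test, and complete, normal data with equal covariance in the two arms. The plan does not say whether time is categorical. If it is, group by time has 3 − 1 = 2 df for the subset markers and 8 − 1 = 7 df for the laboratory values. A linear trend would have 1 df.

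**Formula.** With n per arm and a saturated mean, the sandwich for the arm differences uses divisor n where the unbiased covariance uses n − 1. The Wald statistic is therefore n/(n − 1) times Hotelling's two-sample T². With q contrasts and ν = 2n − 2,

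size = P{ F(q, ν − q + 1) > c × [(n − 1)/n] × (ν − q + 1)/(νq) }, where c is the 95% point of chi-square on q df.

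**Starting point.** The plan's 5% is recovered if the unbiased covariance is used with the Hotelling F reference. Simulation at 20 per arm with 2 df gave 5.0%.

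**40-patient markers, 20 per arm, uncorrected.**
- 2 df: 5.9915 × 19/20 = 5.692; × 37/(38 × 2) = 2.771; P(F(2, 37) > 2.771) = **7.6%**.
- 1 df: 3.8415 × 19/20 = 3.649; P(F(1, 38) > 3.649) = **6.4%**.

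Simulation of the same statistic (60,000 runs) gave 7.5% to 7.7% for 2 df. Direct GEE fits with an exchangeable working correlation (2,000 runs) gave 7.65%.

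**Sensitivity of the 2-df figure.** 18 per arm: 7.9%. A 15/25 split: 8.1%. Log-normal data left untransformed: 6.6%.

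**Routine laboratory values, full trial, uncorrected, 7 df.**
- 76 per arm: 14.067 × 75/76 = 13.882; × 144/(150 × 7) = 1.904; P(F(7, 144) > 1.904) = **7.3%**.
- 68 per arm: 14.067 × 67/68 = 13.860; × 128/(134 × 7) = 1.891; P(F(7, 128) > 1.891) = **7.6%**.

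Simulation (20,000 runs) gave 7.4% for both. By contrast, a full-trial outcome with three times (2 df) has size 5.6%, and one with four times (3 df) 5.9%. What matters is the number of subjects relative to the number of contrasts.

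**What a correction achieves at 20 per arm.** In this balanced case Mancl-DeRouen replaces the factor (n − 1)/n by n/(n − 1).

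| Mancl-DeRouen with | 1 df | 2 df | 3 df |
|---|---|---|---|
| chi-square | 5.1% | 5.8% | 6.7% |
| F(q, 38) | 4.5% | 4.7% | 5.1% |

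A corrected covariance still referred to chi-square therefore falls short for multi-df tests. For the 7-df test at 76 per arm, Mancl-DeRouen gives 6.5% with chi-square and 5.7% even with F(7, 150). There the denominator and scale must also allow for the number of contrasts, as Hotelling's F does.

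**The case against.** The strongest reply is that the plan commits to no faulty test. It names neither a sandwich nor a chi-square reference, and placing subjects as random effects is mixed-model language. If a mixed model was meant, the percentages above do not apply, and one of the remedies is close to what is already planned. This stands: the gap is an unspecified method whose usual form misses its level, not a wrong method written down.

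Second, items b and c are labelled exploratory, and the flow markers have per-time t-test or Mann-Whitney comparisons that do not share the problem. Both facts stand and hold the severity down. They do not help IL-6 and NGAL.

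Third, the inflation is modest, and smaller for a linear time trend (6.4%) or for skewed data left untransformed (6.6% for 2 df). That is also true, although each of these still exceeds 5%.

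Two stronger readings are tempting. A reader might quote a range reaching 8.9%, the size of a 3-df joint test of any group difference at 20 per arm. The plan nowhere states that test; for IL-6 and NGAL it names the group-by-time interaction. A reader might also infer that only the 40-patient set is affected and that standard GEE is safe for everything measured in all 152 patients. The sentence covering IL-6/NGAL also covers the eight-time laboratory values, whose 7-df test is inflated by nearly as much.

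**Conclusion.** The point holds as a minor one. If the usual uncorrected sandwich Wald chi-square test is used, the group-by-time test runs at about 7.6% (2 df) or 6.4% (1 df) for the 40-patient markers. It runs at about 7.3% (7 df, 76 per arm) for the routine laboratory values. These figures rest on equal arms, complete and roughly normal data, and categorical time for the multi-df tests. The uncorrected test is itself an assumption, because the plan does not say. The consequence is an excess of roughly 1.4 to 2.6 percentage points in false signals on secondary and exploratory biomarkers. The primary AKI analysis uses other methods and is unaffected, so this does not bear on the trial's main conclusion.

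**What to change.** In section 3.3.3, first state whether a GEE or a mixed model is intended, since subject random effects are not part of a GEE, and whether time is categorical. Then, for items b and c and for the eight-time routine laboratory values, specify one of the following:

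- a REML repeated-measures mixed model with Kenward-Roger degrees of freedom, on the log scale for skewed markers; or
- GEE with a bias-corrected sandwich (such as Mancl-DeRouen) **and** a t/F reference whose degrees of freedom allow for the number of contrasts tested. The corrected covariance alone is not enough.

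The cost is a few lines of text settled before analysis. R is already named in the plan, and neither sample size nor conduct changes. Intervals widen slightly. For a 1-df contrast at 20 per arm, Mancl-DeRouen with t on 38 df is wider than the uncorrected interval by a factor of (20/19) × (2.024/1.960) = 1.087, about 9%.

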3.3.2 Observation indicators

3.3.2.1 Primary Outcomes

Incidence of AKI within 7 days postoperatively

Percentage of subjects who developed new-onset AKI within 7 days postoperatively. AKI diagnosis was determined by clinicians who remained blinded to group assignments, based on the criteria established by the Global Outcomes in Kidney Disease (KDIGO) standards, as specified below (meeting any one criterion suffices):

1) Serum creatinine elevation $\geq 26.5 \mu\text{mol/L}$ within 48 hours; 2) Increase ≥ 1.5 -fold from baseline within 7 days; 3) Urine output reduced to $<0.5 \text{ mL/kg/h}$ for 6 consecutive hours.

Baseline creatinine was defined as the most recent preoperative serum creatinine measurement.

After baseline creatinine levels were obtained, serum creatinine and urine output were measured daily for seven consecutive days postoperatively.

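### The exploratory Spearman correlations have no arm term, mix samples from before and after AKI onset, and use absolute peak creatinine, so they cannot separate a marker–AKI link from a shared treatment effect or a consequence of AKI

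*Combined protocol and SAP*

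**What the plan says.** Section 3.3.2.2, item 9, gives the purpose of the biomarker work: "To comprehensively evaluate patient status and explore the pathogenesis of AKI, this study detected the following biomarkers". For plasma IL-6 and NGAL (9b) and for the flow cytometry markers (9c) the schedule is the same: "Peripheral blood samples were collected at 24h, 48h, and 72h postoperatively and placed in EDTA anticoagulation tubes". No preoperative sample is listed for either. Both items are labelled exploratory and are run in a subset: "A total of 40 patients were selected from the overall sample using stratified random sampling". Arm and Cleveland Clinic risk level are strata for that selection; the split between arms is not stated.

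Section 3.3.3 specifies the correlations in one sentence, which begins "Spearman correlation analysis was employed to investigate associations between immune cell markers" and goes on to "plasma biomarkers (IL-6, NGAL), and clinical outcomes (AKI incidence rate, peak serum creatinine level". It says nothing of treatment arm, of which of the three samples is used, or of the order of sample and AKI. The default two-sided 0.05 level applies unless otherwise specified.

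Section 3.3.2.1 defines the primary outcome as "Percentage of subjects who developed new-onset AKI within 7 days postoperatively". It also supplies what a tighter analysis would need: "serum creatinine and urine output were measured daily for seven consecutive days postoperatively", and "Baseline creatinine was defined as the most recent preoperative serum creatinine measurement".

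**The concern.** Three features leave the correlations hard to interpret.

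- **Arm.** The trial's hypothesis is that ta-VNS dampens inflammation and lowers AKI. If it does, arm moves both marker and outcome, and the two correlate across the 40 patients even when they are unrelated within each arm. A plain Spearman coefficient has no term to remove this.
- **Order in time.** AKI counts from surgery to day 7, while the markers are drawn at 24, 48 and 72 h. Some samples will follow onset. Item 9b itself groups its markers as inflammatory and renal injury indicators, so a raised value after onset may be a result of AKI.
- **Scale of the outcome.** Absolute peak creatinine carries each patient's preoperative level, whereas AKI is defined largely by change from baseline. This does not create a false link. It weakens a true one.

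At stake is how a significant coefficient is read. It would naturally be taken as support for the neuro-immune mechanism, when assignment or reverse order could produce it.

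**Working it through.** **The plan's own figures.** No sample size or power is given for the correlations. The AKI rates used below, 17.1% (ta-VNS) and 37.9% (sham), come from Section IV. They reproduce that section's sample size closely by the unpooled formula: (1.960 + 0.842)² × (0.171 × 0.829 + 0.379 × 0.621) / 0.208² = 68.4 per group against 68 stated; 68 / 0.90 = 75.6, hence 76.

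**Inputs that are assumptions.** 20 patients per arm; marker shifts of 0.5–1.2 SD between arms; AKI timing; creatinine spreads. The documents give none of these.

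**Step 1: size of the arm effect on the outcome.** On a probit scale the design rates differ by z(0.379) − z(0.171) = −0.308 − (−0.950) = 0.64 SD.

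**Step 2: rejection rate with arm left out.** Simulation of a Spearman test at nominal 5% on 40 patients, with no link between marker and outcome within either arm:

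| Marker shift (SD) | AKI yes/no, 17.1% vs 37.9% | Continuous outcome shifted 0.64 SD |
|---|---|---|
| 0.5 | 7% | 7% |
| 0.8 | 9% | 11% |
| 1.0 | 10% | 13% |
| 1.2 | 12% | 16% |

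Repeat simulations agree to within about one percentage point. A partial rank correlation controlling for arm returns the rate to about 5%.

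**Step 3: samples after onset.** Expected AKI cases in the subset: 20 × 0.171 + 20 × 0.379 = 3.4 + 7.6 = 11.0. As an illustration only, let the marker have no effect on AKI, let 50–75% of cases begin before the sample, and let AKI raise the marker by 0.5–1.5 SD. The mean coefficient is then 0.10–0.41, and P < 0.05 occurs in 10–75% of runs. Adjusting for arm does not remove this, because the distortion also arises within each arm. With no onset-time distribution in the documents, this is a range of what could happen and not an estimate.

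**Step 4: absolute peak against ratio.** On the log scale, peak = baseline + ratio. If the marker relates only to the ratio, and baseline and ratio are independent, the correlation seen with the peak is the true one multiplied by SD(ratio) / √(SD(baseline)² + SD(ratio)²). With assumed log-SDs of 0.20–0.25 for baseline and 0.25–0.35 for the ratio:

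- least favourable: 0.25 / √(0.25² + 0.25²) = 0.707, so 0.5 becomes 0.35;
- most favourable: 0.35 / √(0.20² + 0.35²) = 0.868, so 0.5 becomes 0.43.

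Fisher-z power at n = 40, with the Spearman variance 1.06/(n − 3), falls from 90% to 59–78%.

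**Step 5: what a strict pre-onset rule would leave.** If 50–90% of the 11 cases had begun by 48 h (assumed), 11 × 0.50 to 11 × 0.10, or about 1–5 cases, would remain for a 48 h landmark, and no more than that at 72 h.

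**The case against.** The strongest case against is that this is an exploratory analysis in 40 patients, that the plan speaks only of associations, and that the mechanism question does not rest on it. Section 3.3.3 also plans between-arm comparisons of the immune markers at each time point, and GEE models with a group-by-time term for IL-6 and NGAL. Those comparisons follow the randomization and are untouched by the arm problem. This stands, and it limits the consequence. It does not remove the point: the between-arm comparisons show whether ta-VNS moves a marker, and only the correlations ask whether the marker tracks AKI.

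Several stronger readings are tempting, and the documents do not support them.

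- A reader might infer that the correlations can say nothing about pathogenesis. That goes too far. They remain usable as hypothesis-generating evidence, and under log-SDs of 0.15–0.25 (baseline) and 0.2–0.4 (ratio) the absolute peak still correlates 0.61–0.93 with the relative rise. The eGFR entry criterion of at least 60 also narrows the spread of baseline creatinine.
- A reader might take the AKI incidence rate to be a group figure that cannot be ranked. Literally so, but the same section uses AKI incidence as the outcome of a logistic regression, which must be patient-level. It is a wording slip for AKI yes/no.
- A reader might put the false-positive rate as high as 41%. That needs arm shifts of 1.2 SD in both marker and outcome; the design rates imply about 0.64 SD for the outcome.
- A reader might say that the plan pools the arms. It does not say so. The point rests on its silence.

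The objection that a strict pre-onset rule at 48 h and 72 h would leave too few cases also stands, and it shapes the fix.

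**Conclusion.** The concern holds in a limited form. As written, the correlations cannot distinguish a marker–AKI link from a shared effect of ta-VNS or from a consequence of AKI. Leaving out arm inflates the 5% test modestly: to about 7–12% for AKI yes/no at the design rates, and about 7–16% for a continuous outcome shifted 0.64 SD. Both ranges assume marker shifts of 0.5–1.2 SD and 20 patients per arm. Post-onset sampling could be the larger problem, but its size cannot be fixed from the documents because they give no onset timing. Absolute peak creatinine costs power and does not itself produce false links; the fall from 0.5 to 0.35–0.43 depends on the assumed spreads. No primary or safety conclusion is affected. The change is still worth making before analysis, since the data needed are already collected.

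**What to change.** Amend the correlation paragraph in Section 3.3.3 to:

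- use partial Spearman correlations controlling for arm;
- define the outcomes as patient-level AKI within 7 days (yes/no) and the ratio of peak to baseline creatinine;
- make the 24 h sample, in patients without AKI by 24 h, the main pathogenesis analysis, and state how onset is placed relative to the sample given daily assessment;
- keep the 48 h and 72 h correlations, but label those that include post-onset samples as marker response;
- report all of them as hypothesis-generating.

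This needs SAP wording only and no new data. The cost is that the 24 h landmark drops early AKI cases from an expected total of about 11, so intervals widen and the result speaks only to AKI arising after 24 h. How many cases would be lost cannot be computed from the documents.

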3.2.3 Exit Criteria

1) The subject or their legal representative requests to withdraw from the study.

- 2) Development of intolerable ta-VNS-related adverse reactions (e.g., severe skin hypersensitivity, pain, dizziness, etc.).
- 3) Perioperative changes in condition (e.g., prolonged sedation, reoperation) render continued stimulation unfeasible.
- 4) The investigator determined that the subject was not suitable to continue participating in the study.

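### The minimum-stimulation-days analysis counts days after AKI onset as preventive dose, so it can show a false protective dose-response and plateau if completion falls with AKI or with severity

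*Combined protocol and SAP*

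**What the plan says.** Section 3.3.3 (Statistical Analysis Plan) gives the purpose of this analysis as "To determine the minimum number of stimulation days required to achieve clinical efficacy". A day counts as completed when at least 80% of its planned stimulation time was delivered. The exposure is then formed "Based on the total number of days (0-6 days) during which subjects completed stimulation", and a multivariate logistic model is to examine "the dose-response relationship between cumulative stimulation days and the incidence of AKI, thereby identifying the critical number of days" beyond which protection levels off. The section names no covariates for this model. It does not say whether sham patients enter it, and it does not call the analysis exploratory.

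Three other sections bear on timing and on who misses days:

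- Section 3.3.1 schedules stimulation on the day of surgery and on postoperative days 1 to 5, and has it stopped for persistent heart rate below 50, significant hemodynamic instability or other severe adverse events.
- Section 3.3.2.1 defines the outcome as "Percentage of subjects who developed new-onset AKI within 7 days postoperatively", with creatinine and urine output measured daily.
- Section 3.2.3 lists as an exit criterion: "Perioperative changes in condition (e.g., prolonged sedation, reoperation) render continued stimulation unfeasible".

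**The concern.** Exposure and outcome build up over the same days. For a patient with AKI on postoperative day 1, sessions on days 2 to 5 make up four of the six possible days of dose, yet none of them can have prevented that AKI. If such patients complete fewer of those sessions, a low count is partly a consequence of the outcome. Covariate adjustment in a logistic model does not undo that.

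A second route needs no reverse causation. Prolonged sedation, reoperation and hemodynamic instability end or interrupt stimulation, and they mark a difficult course in which AKI is also more likely. Days completed would then stand in for severity.

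At stake is a stated number of days needed for efficacy. If that number reflects who could complete sessions rather than what the sessions did, it could still be carried into practice or into the design of a later trial.

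**Working it through.** **Inputs from the documents.** Six possible days (day 0 to day 5). AKI window of 7 days. Pilot AKI rates of 17.1% (ta-VNS) and 37.9% (sham), two-sided alpha 0.05, and 76 patients per arm (section IV: 68 / 0.90 = 75.6, rounded up to 76). The plan gives no figure of its own for the dose-response analysis.

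**Assumptions, not in the documents.** AKI onset on days 0/1/2/3/4 with probabilities 0.10/0.40/0.30/0.15/0.05. Daily completion of 90% or 95% before AKI, lower by a fixed number of points on days after onset. No treatment effect.

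**Why a small fall matters.** The mean number of scheduled days after the onset day is 0.10×5 + 0.40×4 + 0.30×3 + 0.15×2 + 0.05×1 = 3.35. A 10-point fall therefore costs an AKI patient 3.35 × 0.10 = 0.335 completed days on average. Without AKI, the standard deviation of completed days is √(6×0.95×0.05) = 0.53 at 95% completion and √(6×0.90×0.10) = 0.73 at 90%. The shift is thus about 0.6 or 0.5 of a standard deviation, produced with no treatment effect.

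**Simulation.** Model: logit P(AKI) = a + b × (total completed days), 76 active patients, unadjusted. Ranges span AKI rates of 17.1% to 37.9% and completion before AKI of 90% to 95%.

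| Fall in daily completion after AKI | OR per day (true value 1.0) | Trials with a significant protective slope |
|---|---|---|
| None | about 1.0 | 2-3% |
| 5 points | 0.6-0.8 | 12-22% |
| 10 points | 0.4-0.6 | 32-60% |
| 20 points | 0.3-0.4 | 71-96% |

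The nominal rate in one direction is 2.5%, so the first row behaves as it should.

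**Other assumptions.** These runs use onset on days 0 to 6 of 25/35/25/8/4/2/1%, 90% completion before AKI and an AKI rate of 27.5% (midpoint of the pilot rates).

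- Completion rising to 95% after AKI: OR 1.47, the opposite direction.
- Completion falling to 70%: AKI risk at 3/4/5/6 completed days is 0.73/0.51/0.29/0.14, a steep dose-response with no effect behind it. With uniform onset over days 0 to 6 the OR is 0.55 rather than 0.39.
- Shared severity only, with no fall after AKI (log-odds 0.5 to 1 per SD): OR 0.81 to 0.60, significant in 10% to 53% of trials.
- Sham patients pooled as 0 days, completion 70% after AKI: OR 0.95 without an arm term and 0.39 with one.

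**Check of alternatives**, same assumptions. A person-day logistic model in patients still AKI-free, with days completed to the previous day and adjusted for day, gives OR 1.01, 1.01 and 0.99 when completion after AKI is 80%, 70% and 50%. The model as planned gives 0.59, 0.40 and 0.22. Under shared severity (log-odds 1 per SD) the person-day model gives 0.56 against 0.60 as planned, so that confounding stays. Keeping the planned model and simply stopping the count at onset makes matters worse (OR 0.07-0.09), because early AKI then forces a low count.

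**The case against.** The strongest reply is that the documents never link AKI to missed sessions. The exit criterion gives prolonged sedation and reoperation as examples, and the discontinuation rule in section 3.3.1 names low heart rate, instability and severe adverse events. AKI here can be six hours of low urine output or a creatinine rise of 26.5 µmol/L, and nothing in the text makes either a reason to stop stimulating the ear. No completion rates are given by AKI status.

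This stands against a stronger reading. A reader might infer that the analysis is bound to show protection even if ta-VNS does nothing, or that patients with AKI are by rule the ones whose sessions stop. The documents support neither. The fall in completion is assumed, and the stopping rules support confounding by severity more directly than reverse causation.

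It is also fair to say that the analysis lies outside the objectives in section II and the outcomes listed in section 3.3.2, and that pooling sham patients as zero days without an arm term would dilute the slope.

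None of this rescues the inference. A plateau whose size and even direction depend on unknown completion behaviour cannot identify a minimum effective duration.

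**Conclusion.** The concern holds in conditional form. As written, the analysis can, and plausibly will, show a spurious protective dose-response and plateau if completion falls with AKI or with its underlying severity. It shows none if completion is unrelated to AKI.

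The sizes in the table rest on assumed onset days and completion rates, an unadjusted model and active patients only. A 5-point fall leaves the false-positive share modest; a 20-point fall makes a false finding likely. The structural fault, counting days after onset as preventive dose, is plain in the text and needs no assumption.

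This should be fixed, but it does not threaten the trial's main result: the primary comparison is randomised and analysed by intention to treat, and does not use days completed.

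**What to change.** Delete from section 3.3.3 the statements that this analysis will determine the minimum number of stimulation days or the number at which protection plateaus. If an exploratory look is kept, specify that:

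- it is hypothesis-generating;
- it is a person-day logistic model in patients still AKI-free, with exposure equal to days completed up to the previous day, adjusted for day and a short, named list of baseline risk factors;
- it is fitted in the ta-VNS arm, and the same model is fitted in the sham arm as a negative control, where device-off sessions should show no slope;
- confounding by severity remains; the sham arm can reveal it but not correct it.

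The person-day form is preferable to separate landmarks. With 20% of onsets after day 2, the active arm would have 76 × 0.171 × 0.20 = 2.6 to 76 × 0.379 × 0.20 = 5.8 events left, about 3 to 6. Even the person-day model has few events (13.0 to 28.8 AKI cases in the arm, less those on day 0), so adjustment must be sparing.

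The cost is SAP wording. The 80% completion rule already requires daily stimulation time, and AKI is already assessed daily. The trial gives up a statement on minimum duration, which this design cannot support.
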